## **6.6. Safety Analysis Set [SAF]**

The Safety Analysis Set will consist of all randomized participants who received at least one dose of randomized study medication, as determined on the drug accountability eCRF page (i.e., participants are expected to either have a date of first dose or indicate that no study medication has been taken).

### **6.7. Safety Follow-up Analysis Set [SFAS]**

The Safety Follow-up Analysis Set will contain all randomized participants who receive at least one dose of study medication and had at least one diary entry for DYS or NMPP after the date of last treatment.

### **6.8. Pharmacokinetic Analysis Set**

The PK analysis set is a subset of the safety analysis set (SAF) and will include all participants who received at least one dose of OG-6219 and have at least 1 quantifiable OG-6219 or FOR-1011 concentration, which is not impacted by protocol violations or events with potential to affect the PK.

### **6.9. Pharmacokinetic Analysis Set for Noncompartmental Analysis**

The PK analysis set for noncompartmental analysis (NCA) will include all participants in the PK analysis set who chose intensive PK sampling in Day 1 (V4) and V5 and have sufficient samples to determine at least one PK parameter for OG-6219 or FOR-1011. Intensive PK sampling is optional where a separate consent would be provided.

### **6.10. Pharmacodynamic Analysis Set**

The Pharmacodynamic Analysis Set is a subset of the SAF and will include all participants who took at least one dose of OG-6219 or Placebo and have at least one quantifiable PD endpoint without protocol deviations or events affecting the PD results.

## **7. PLANNED ANALYSES AND DATA MONITORING**

### **7.1. Interim Analysis and Early Stopping Guidelines**

A Data Monitoring Committee (DMC) will review unblinded safety data during the study. The planned safety analyses for DMC are described in a separate DMC SAP, and are not in scope for this SAP.

An interim psychometric analysis using blinded data will be performed to affirm methods for

establishing pain responder cutoffs. The interim psychometric analysis will be conducted by Adelphi Values under a separate SAP.

An interim PK and exposure-response modelling analysis will be performed by Certara using unblinded data. This analysis is described in a separate PK modelling plan.

## **7.2. Final Analysis**

All planned analyses identified in this SAP will be performed by the ORD Biostatistics and Programming team following authorization of this SAP, database lock, and unblinding.

Final psychometric analyses, PK analyses, and exposure-response modelling analyses are not in scope for this SAP.

# **8. STATISTICAL METHODS**

## **8.1. General Methodology**

### **8.1.1. Summary tables, listings, and figures**

All data will be listed and summarized with descriptive statistics in summary tables.

Continuous variables will be summarized for both the measured values and the change from baseline value, using the number of observations, mean, standard deviation (SD), median, minimum, and maximum. Categorical and ordinal variables will be summarized with counts and percentage for each category.

Box-and-whisker plots will be used to visualize efficacy endpoints by timepoint and treatment. Box-and-whisker plots will also be used to visualize laboratory data, vital signs, and ECG measurements. The results of the main efficacy analyses will be illustrated by plotting differences vs. placebo with 95% CIs for each OG-6219 dose group vs. cycle (or visit).

Mean values for each day relative randomization will be plotted by treatment group for OPP, number of rescue medication tablets used, and interference with daily activities.

### 8.1.2. Reference Start Date and Study Day

Study Day will be calculated from the reference start date and will be used to show start/stop day of assessments and events. Reference start date (Day 1) is defined as the day CCI, which is also the first dose of randomized study medication.

### 8.1.3. Baseline and Change from Baseline

Baseline is defined as the last non-missing measurement (including unscheduled assessments) taken prior to first dose of randomized study medication (reference start date).

In the case where the last non-missing measurement and the reference start date coincide, that measurement will be considered pre-baseline with the following exceptions:

Adverse Events (AEs) and medications commencing on the reference start date will be considered as either pre-baseline or post-baseline based on the collected eCRF assessment of whether the item started prior to the start of study medication.

Visit 4 measurements scheduled to be made after first dose of randomized study medication (e.g. post-dose ECG measurements) will be regarded as post-baseline. Baseline ECG is the average of the triplicates taken prior to first dose of randomized study medication.

For related assessments (e.g., systolic and diastolic blood pressure), it is desirable that all baseline values come from the same measurement date and not from different dates/visits in case one value is missing. In the event where one value is missing, values from the same measurement dates will be used.

For HRQoL, Fatigue, and Productivity Questionnaires (EHP-30, EQ-5D-5L, WPAI-Endometriosis, PROMIS Fatigue Short Form 6a, and PGI-S) assessments collected on CCI will be considered Baseline. In case data were not entered CCI but within a few days from visit 4, these data will still be considered as baseline.

### 8.1.4. Retests, Unscheduled Visits and Early Termination Data

For by-visit summaries, only scheduled time points will be included. In the case of a retest (same visit number assigned and same date), the last available measurement for that visit will be used for by-visit summaries.

Listings will include scheduled, unscheduled, retest and early discontinuation data.

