- ECG findings of QTcF prolongation of **CCI**, or a change of >60 ms from the pre-dose ECG, based on the average of triplicate ECGs
- Participants who experience suicidal ideation or attempt suicide
- Safety recommendation based on DMC / investigator/ Sponsor assessment of AEs and AESI
- If the participant becomes pregnant at any time after providing a signed ICF, the participant must be withdrawn immediately and if the participant has received at least 1 dose of experimental study treatment the participant must be followed through the pregnancy (refer to [Appendix 5](#)).
- If the participant undergoes urgent surgical procedures for endometriosis-related pain.
- The participant was erroneously included in the study (failed to meet protocol entry criteria)
- Participants whose treatment assignment has intentionally been unblinded by the Investigator
- The participant participates in another investigational study
- The participant is unable to comply with protocol requirements (eg, eDiary compliance, use of study treatment, use of rescue and prohibited medication, etc.)

Participants removed from study treatment for any reason will undergo the assessments for the discontinuation Visit (SoA, Section 1.3) and will have a Follow-up Visit to assess safety after completing 1 full cycle after the participant's last dose of study treatment.

A participant will be considered "discontinued due to an AE" if she withdraws from the study due to any AE, regardless of whether or not the AE is considered related to study treatment. If the participant withdraws from the study due to an AE, the Investigator should arrange for the participant to be followed appropriately until the AE has resolved or stabilized (in the opinion of the Investigator).

Decisions about medical care after study treatment discontinuation will be made according to Investigator's opinion.

The Investigator will document the reason(s) for treatment or study discontinuation. The Medical Monitor should be informed when a participant is withdrawn from the study.

Participants who do not wish to conceive after the last dose of study treatment should begin a new contraceptive method as soon as possible. Post-study contraceptive counseling will be provided by study site personnel in accordance with the SoA (Section 1.3).

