8.3.7 Clinical Safety Laboratory Tests

CCI, clinical chemistry, urinalysis, serology, and additional laboratory parameters to be tested during the study are listed in [Appendix 3](#). At Screening and the EOS Visit, participants are required to be in a fasted state at the time of the laboratory sample (with fasting defined as at least 8 hours following the last meal or snack). At all other scheduled visits, participants do not need to be in a fasted state; however, fasting status will be documented. At least 1 backup aliquot at each visit will be stored for potential further assessments.

Laboratory samples will be analyzed by a central laboratory. Laboratory tests may be repeated at any visit if there was an abnormal finding at the most recent previous evaluation or if additional information is clinically necessary to appropriately evaluate the participant's current condition, follow-up, and/or manage an AE.

The Investigator will review laboratory results with a frequency that ensures participants safety. Clinically significant changes from Screening in laboratory results must be considered

an AE and recorded in the eCRF. Clinical significance is defined as any variation in a laboratory result that has medical relevance and that results in a change in medical care. The Investigator will continue to monitor the participant until the finding is resolved or, in the judgment of the Investigator, follow-up is no longer medically necessary.

Local assessment of clinical laboratory parameters is permitted when these data are required for safety reasons in a timeframe faster than the central laboratory can provide.

Specific withdrawal criteria for liver enzymes are presented in the Withdrawal Section 7.0.

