### 8.7.2. Laboratory Evaluations

Quantitative laboratory measurements reported as '< X', i.e., below the lower limit of normal (LLN), or '> X', i.e., above the upper limit of normal (ULN), will be converted to X for the purpose of quantitative summaries, but will be presented as recorded, i.e., as '< X' or '> X' in the listings. If local and central laboratory assessments are available from the same day, central laboratory assessments will be used in the summary.

The following summaries will be provided for laboratory data:

- Observed values and change from baseline by visit for Chemistry, Hematology and Urinalysis (quantitative measurements)
- Observed values for categorical measurements
- Shift from baseline value to each post-baseline visit value according to normal range criteria (quantitative measurements and categorical measurements)

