### 8.7.3. ECG Evaluations

The following ECGs measurements will be reported for this study:

- Axis (degree)
- Heart Rate [beats per minute (bpm)]
- PR Interval (msec)
- QT Interval (msec)
- QTcB Interval (msec)
- QRS Interval (msec)
- RR interval (msec)
- QTcF Interval (msec)
- Overall interpretation of ECG:
  - Normal
  - Abnormal, Not Clinically Significant (Abnormal NCS)
  - Abnormal, Clinically Significant (Abnormal CS)

Triplicate standard 12-lead ECGs will be obtained after the participant has been in a supine position for at least 5 minutes. ECG measurements will be summarized by taking the average of the available assessments.

The following summaries will be provided for ECGs data:

- Observed values and change from baseline by visit and timepoint
- Shift in normal/abnormal NCS/abnormal CS in the overall interpretation from baseline to each timepoint

The number of participants with absolute QTcF values CCI, and the number of participants with change from baseline in QTcF, CCI during

treatment will be summarized by treatment group. QTcF prolongation is defined as CCI or a change CCI.

A scatter plot will be presented, showing baseline QTcF on the x-axis, post-baseline QTcF on the y-axis (one panel for each treatment), and diagonal lines indicating changes of -60, -30, 0, +30, and +60. Different symbols will be used to identify the different post-treatment timepoints.

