#### 8.7.4. Vital Signs

The following Vital Signs measurements will be reported for this study:

- Systolic Blood Pressure (mmHg)
- Diastolic Blood Pressure (mmHg)
- Heart Rate (bpm)
- Respiratory rate (breaths/min)
- Body temperature (°C)
- Weight (kg)
- BMI (kg/m^2)
  - Observed values and changes from baseline will be presented by visit and treatment group.

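### As SAP 8.1.4 is written, laboratory and ECG results from the discontinuation visit and from unscheduled samples enter no by-visit or shift table

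*SAP*

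**What the plan says.** SAP 8.1.4 gives two destinations for safety results. On tables it says "For by-visit summaries, only scheduled time points will be included". On listings it says "Listings will include scheduled, unscheduled, retest and early discontinuation data". A retest under the same visit number and date does enter the by-visit tables, where the last value is used.

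The tables that depend on this rule are these:
- **Laboratory (SAP 8.7.2):** observed values and changes by visit, and "Shift from baseline value to each post-baseline visit value according to normal range criteria".
- **ECG (SAP 8.7.3):** changes by visit and timepoint, and "Shift in normal/abnormal NCS/abnormal CS in the overall interpretation from baseline to each timepoint".
- **Vital signs (SAP 8.7.4):** "Observed values and changes from baseline will be presented by visit and treatment group".

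The protocol plans to collect results outside the regular visits. Section 7.2 says "Participants removed from study treatment for any reason will undergo the assessments for the discontinuation Visit". The Discontinuation column of the Schedule of Activities (Protocol 1.3) is marked for hematology and chemistry, urinalysis and ECG. Protocol 8.3.7 adds "Laboratory tests may be repeated at any visit if there was an abnormal finding at the most recent previous evaluation".

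**The concern.** Abnormalities in laboratory assessments are part of the primary safety endpoint (Protocol 3.0, Table 1). A woman who stops treatment, or who is called back for an extra sample, is more likely than average to have an abnormal value on that occasion. If those results are left out of the by-arm shift tables, the omission is not random. It grows with the rate of stopping, so it would be largest in an arm where the drug itself causes stopping.

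The rule is also one-sided. SAP 8.1.3 lets unscheduled assessments define baseline, whereas 8.1.4 does not let them into the post-baseline by-visit tables.

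**Working it through.** **Step 1: which tables can take the values.** Each by-arm safety summary in the SAP, set against the 8.1.4 rule:

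| Summary | Tied to visit or timepoint? | Can a discontinuation or unscheduled result enter? |
|---|---|---|
| Laboratory values, changes and shifts (8.7.2) | Yes | No, as written |
| Categorical laboratory values (8.7.2) | Not stated | Not stated |
| ECG changes and shifts (8.7.3) | Yes | No, as written |
| Vital signs (8.7.4) | Yes | No, as written |
| Liver thresholds (8.7.2.2) | No, post-baseline results | Yes, but not stated that all results count |
| QTcF counts (8.7.3) | No, during treatment | Yes, but not stated that all results count |
| C-SSRS (8.7.6.4) | No, any post-baseline assessment | Yes |
| TEAE and AESI tables (8.7.1) | No | Yes, if recorded as an AE or AESI |

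**Step 2: two women traced through the tables.**
- *Woman A* is stopped because her hemoglobin has fallen. Her care changed, so under Protocol 8.3.7 the finding is an AE. She is counted in the TEAE table and in the table of TEAEs leading to discontinuation (SAP 8.7.1.1, 8.7.1.2), and as an AESI if three of the four hemolysis criteria are met and the event is recorded as one (8.7.1.6). She is missing only from the shift table.
- *Woman B* stops for another reason, and her discontinuation sample is below the reference range. The investigator does not judge it clinically significant, and fewer than three hemolysis criteria are met. She has no AE and no AESI, and her abnormal value enters no by-visit or shift table. Her later follow-up visit comes a full cycle after the last dose (Protocol 7.2), so it may show recovery rather than the value at stopping.

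Woman B is the case that the plan misses. The primary endpoint is abnormalities, which is wider than investigator-judged AEs.

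**Step 3: size.** The only relevant figure in the documents is the dropout rate in SAP 4.3, which gives 95 per arm, a difference of 1, SD 2.2, 2-sided 0.05, 10% dropout and 84% power. To check that the 10% is the working figure:
- n per arm after dropout = 95 × (1 − 0.10) = 85.5
- power = Φ(1 / (2.2 × √(2/85.5)) − 1.96) = Φ(2.97 − 1.96) = 0.844, which agrees with the stated 84%.

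With dropout as a stand-in for women who have a discontinuation visit:
- at 10%: 0.10 × 380 = 38 women, or 0.10 × 95 = 9.5 per arm
- at an assumed 5%: 19 women, about 5 per arm
- at an assumed 20%: 76 women, 19 per arm.

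At each dropout rate the count is a ceiling. Protocol 7.2 holds the early discontinuation visit only if possible, and women lost to follow-up may have no values at stopping. If half of the 10% had the visit (assumption), the number would be 19.

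**The case against.** The strongest reply has four parts.

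1. **The exclusion is inferred.** The SAP never defines a scheduled time point, and the discontinuation visit has its own column in the Schedule of Activities. The sentence on listings does not say that listings are the only destination. This stands as a caution. But 8.1.4 names early-discontinuation data separately from scheduled data and gives no mapping rule, so a programmer following it would leave them out.

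2. **Other by-arm tables carry the important events.** This stands in large part. A reader might infer that safety data at stopping reach listings only, and that harm is hidden. The documents do not support that. Suppose 3 of 95 women (3.2%) were stopped for a hemoglobin fall seen only off-schedule. The shift table would show none of them, but all three would be Woman A above, counted in the TEAE and discontinuation tables.

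3. **Vital signs.** A reader might also assume that vital signs are taken at stopping. The Schedule of Activities, as extracted, has no mark for them in the Discontinuation column, although a broken table is possible. What remains is that unscheduled vital signs reach no vital-sign table.

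4. **Women who stop are not wholly absent from later rows.** Protocol 7.1 keeps them in the study for safety and 7.2 plans a follow-up visit, though 7.2 also says that treatment and study end together, and these statements need reconciling. Follow-up values can enter the tables, but they are not the values at stopping.

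**Conclusion.** The point holds for laboratory and ECG results. On the natural reading of SAP 8.1.4, results from the discontinuation visit and from unscheduled samples are left out of the by-visit and shift tables, and nothing elsewhere in the SAP brings them back into those tables. The laboratory shift tables for the primary safety endpoint can understate abnormalities, selectively in an arm where the drug causes stopping.

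The loss is confined to those tables. It falls mainly on values outside the reference range that were not judged clinically significant. The number of women is not known: the 38 of 380 assumes that dropout equals treatment discontinuation and that every such woman attended the visit. This is an inexpensive improvement that should be made. It is not evidence that the plan conceals serious harm.

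**What to change.** Keep the by-visit tables and make four changes to the SAP:

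1. **8.7.2 and 8.7.3:** add a shift from baseline to worst post-baseline value, by arm, with separate low and high directions for two-sided parameters. Use all scheduled, unscheduled, retest and discontinuation results from the first randomised dose to 14 days after the last dose, which matches the TEAE window in 8.7.1.
2. **8.1.4:** state how discontinuation-visit results are mapped, for example to a last-on-treatment row.
3. **8.7.2.2 and the QTcF counts in 8.7.3:** state that all post-baseline results are used, whether scheduled or not.
4. **Endpoint link:** use the laboratory worst-value shift to report the primary safety endpoint on laboratory abnormalities. Do not use it as the measure of secondary safety endpoint 9. That endpoint rests on clinical significance, meaning medical relevance and a possible change in care, and a reference-range shift does not measure this.

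The cost is SAP wording and a few more tables, with two directions for some parameters. The data are already collected, so no protocol amendment is needed. Worst-value tables will raise abnormality rates slightly in every arm, placebo included, so they should be read as comparisons between arms.

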#### **8.1.5. Imputation of Missing Data**

All data will be evaluated as observed and no imputation methods will be used.

#### **8.1.6. Intercurrent Events**

Intercurrent events for the include premature treatment discontinuation for any reason, including adverse event or lack of efficacy. Data after the last day of treatment will not be included in TRC1-TRC3, but only in SFC. A hypothetical strategy will be used in the statistical analyses, assuming that premature treatment discontinuation did not occur and therefore all participants completed the treatment period. Consequently, if the mean score for TRC2 and/or TRC3 cannot be calculated, data will be assumed to be missing at random (MAR).

Use of study supplied rescue medication for ERP per the protocol is not considered to be an intercurrent event. Also, use of prohibited pain medication is not considered to be an intercurrent event. In clinical practice, use of rescue medication and pain medication cannot be restricted for subjects with endometriosis. Therefore, treatment effects must be evaluated in the presence of these additional medications.

#### **8.1.7. Multiple Comparisons/Multiplicity**

There will be no adjustments for multiple comparisons. The three doses of OG-6219 will be compared to placebo pairwise without any adjustments for multiplicity. Nominal p-values will be reported.

### **8.2. Study Participants**

#### **8.2.1. Disposition of Participants**

Participant disposition and withdrawals, and reasons for exclusion from each analysis set will be presented for the ENR set.

The number and percentage of participants who were screened, screen failed (including reason screen failed), allocated to treatment, completed, or discontinued the randomized treatment period (including reasons for treatment discontinuation), completed or withdrew from the study, (including reasons for study withdrawal) will be presented.

In addition, the primary reason for discontinuation for participants who were allocated to study treatment but discontinued prior to study treatment (participants did not receive study treatment) will be presented. Participants who did not receive study treatment will be identified by “no study drug taken” indicated on the Drug Accountability CRF. Completion of treatment and completion of study are recorded on the End of Study Treatment and Disposition eCRF pages, respectively.

#### 8.2.2. Protocol Deviations

The IQVIA Clinical Trial Management System (CTMS) will collect protocol deviations and as per the Protocol Deviation Management Plan.

The number of participants with at least one protocol deviation, and the number of participants with at least one critical or major protocol deviation, will be summarized by deviation category as described in the PDMP for the FAS. Protocol deviations which lead to exclusion from the PP will be summarized.

All critical and major protocol deviations will be listed.

